A sample size of 72 in Cohort 1 and 150 in Cohort 2 is sufficient to detect with reasonable power the antiviral effect; even if the data of Cohort 1 cannot be combined with the data of Cohort 2. Therefore, the primary analysis will be performed after approximately 150 subjects from Cohort 2 have completed the Day 14 assessments (or discontinued earlier). By that time, it is expected that at least 72 subjects from Cohort 1 will have completed the Day 14 assessments (or discontinued earlier).

For Cohort 1, assuming a median time to resolution of symptoms of 3 days in the placebo group, a 1-day reduction in the active group (i.e. ratio of 66%), and a scale parameter of 1/0.65, a sample size of 48 subjects per treatment arm will achieve 95% probability to reach an observed effect in the right direction based on estimates derived from an accelerated failure time model. This will allow an adequate evaluation of clinical course endpoints in the hospital population.

In conclusion, approximately 144 subjects in Cohort 1 (48 subjects per treatment arm) and approximately 150 in Cohort 2 (50 subjects per treatment arm) are planned to be recruited. The sample size of Cohort 2 may be re-estimated to a maximum of 300 in Cohort 2 based upon results from the third IA.

Sample Size Re-estimation

During IA#3 (when approximately 70 to 80 subjects from Cohort 2 have completed the Day 14 assessments [or discontinued earlier]), a sample size re-estimation will be performed to allow an extension of Cohort 2 for the confirmation of the results on selected

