Table 4: Planned Collection of PRESORS ClinRO, PRESORS ObsRO and Clinical Evaluation

Assessments	Cohort 1		Cohort 2
	During Hospitalization	After Discharge	
PRESORS ClinRO	BID from Day 1 to Day 14 and QD from Day 15 to Day 21	Once at clinic visits	Once at clinic visits
Clinical Evaluation^f/ SBP+DBP	BID from Day 1 to Day 21 + Day 28*	Once at clinic visits + Day 28*	Once at clinic visits + Day 28*
PRESORS ObsRO	BID from Day 1 to Day 14 and QD from Day 15 to Day 21		
Body Temp Caregiver	NA	BID from Day 2 to Day 14 and QD from Day 15 to Day 21	BID from Day 1 to Day 14 and QD from Day 15 to Day 21

^f Clinical evaluation includes respiratory rate, heart rate, body temperature, and SpO2.

* Only in case of on-site visit.

Visit windows for these assessments are defined as in **Table 5**.

Table 5: Visit Windows for PRESORS ClinRO, PRESORS ObsRO, Clinical Evaluation (including SBP/DBP) and Body Temperature

Analysis Time	Time Interval	Target Time
Baseline		0
12h (Day 1.5)	>0h [§] ; 17h59min	12h
24h (Day 2.0)	18h; 29h 59 min	24h
36h (Day 2.5)	30h; 41h 59min	36h
48h (Day 3.0)	42h; 53h 59min	48h
60h (Day 3.5)	54h; 65h 59min	60h
72h (Day 4.0)	66h; 77h 59min	72h
84h (Day 4.5)	78h; 89h 59min	84h
96h (Day 5.0)	90h; 101h 59min	96h
108h (Day 5.5)	102h; 113h 59min	108h
120h (Day 6.0)	114h; 125h 59min	120h
132h (Day 6.5)	126h; 137h 59min	132h
144h (Day 7.0)	138h; 149h 59min	144h
156h (Day 7.5)	150h; 161h 59min	156h
168h (Day 8.0)	162h; 173h 59min	168h
180h (Day 8.5)	174h; 185h 59min	180h
192h (Day 9.0)	186h; 197h 59min	192h
204h (Day 9.5)	198h; 209h 59min	204h
216h (Day 10.0)	210h; 221h 59min	216h
228h (Day 10.5)	222h; 233h 59 min	228h
240h (Day 11.0)	234h; 245h 59min	240h
252h (Day 11.5)	246h; 257h 59min	252h
264h (Day 12.0)	258h; 269h 59min	264h
276h (Day 12.5)	270h; 281h 59min	276h
288h (Day 13.0)	282h; 293h 59 min	288h

Table 5: Visit Windows for PRESORS ClinRO, PRESORS ObsRO, Clinical Evaluation (including SBP/DBP) and Body Temperature

Analysis Time	Time Interval	Target Time
300h (Day 13.5)	294h; 305h 59min	300h
312h (Day 14.0)	306h; 317h 59min	312h
Day 15	Day [15] (2 AM-1:59 AM)	15
Day 16	Day [16] (2 AM-1:59 AM)	16
Day 17	Day [17] (2 AM-1:59 AM)	17
Day 18	Day [18] (2 AM-1:59 AM)	18
Day 19	Day [19] (2 AM-1:59 AM)	19
Day 20	Day [20] (2 AM-1:59 AM)	20
Day 21	Day [21] (2 AM-1:59 AM)	21
Day 22	Day [22] (2 AM-1:59 AM)	22
Day 23	Day [23] (2 AM-1:59 AM)	23
Day 24	Day [24] (2 AM-1:59 AM)	24
Day 28	Day [25, $+\infty$] (2 AM-1:59 AM)	28

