	
The approximate 24h symptoms resolution is defined with the following considerations:
 
 • Three consecutive recordings indicating resolution are required, if the first (of these 3 consecutive) recording is before the second analysis timepoint of the BID schedule at Day 14. These 3 consecutive recordings should have been done over 4 scheduled consecutive analysis timepoints, 1 missing timepoint is allowed. • Two consecutive recordings indicating resolution are required, if the first (of these 2 consecutive) recording is at or after the second analysis timepoint of the BID schedule at Day 14. These 2 consecutive recordings should have been done over 3 scheduled consecutive analysis timepoints, 1 missing timepoint is allowed 
In case RSV symptoms (concepts) are not resolved, data will be censored as follows:
 
  
 Situation	Censoring	
   
 Last ObsRO assessment indicates resolution of RSV symptoms but insufficient recordings to meet the time to resolution requirement (24h)	Censored at first record of resolution from the last series of recordings of resolution of RSV symptoms (concepts)	
 
 Last ObsRO assessment does not indicate resolution of RSV symptoms	 
After the last observation, censored at 08:00 on the same day if the last observation was a morning diary entry (from 00:00 until 01:59)
 
After the last observation, censored at 20:00 on the same day if the last observation was a morning diary entry (from 02:00 until 13:59)
 
Censored at 8:00 the next day if the last entry was an evening diary entry (from 14:00 until 23:59)
 	
 
 Death (without previous resolution)	Censored at date/time of death	
 
 Missing information to determine resolution of symptoms (concepts) because of (re-)hospitalization (without previous resolution)	Censored at date/time of (re-)hospitalization	
  
 
time to event (hours) = (date/time of event or censoring – date/time of first dose of study drug)/3600, rounded to one decimal
	Situation	Censoring	Last ObsRO assessment indicates resolution of RSV symptoms but insufficient recordings to meet the time to resolution requirement (24h)	Censored at first record of resolution from the last series of recordings of resolution of RSV symptoms (concepts)	Last ObsRO assessment does not indicate resolution of RSV symptoms	
After the last observation, censored at 08:00 on the same day if the last observation was a morning diary entry (from 00:00 until 01:59)
 
After the last observation, censored at 20:00 on the same day if the last observation was a morning diary entry (from 02:00 until 13:59)
 
Censored at 8:00 the next day if the last entry was an evening diary entry (from 14:00 until 23:59)
	Death (without previous resolution)	Censored at date/time of death	Missing information to determine resolution of symptoms (concepts) because of (re-)hospitalization (without previous resolution)	Censored at date/time of (re-)hospitalization

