Sustained resolution of RSV [summary parameter] [categorical]	
RSV summary parameters:
 
 • Key RSV symptoms • Overall RSV symptoms 
Sustained resolution, assessed over entire study course, is defined as no evidence of recurrence once resolution has been reached and where:
 
 • Resolution is considered when All individual RSV concepts comprising relevant summary parameter are scored as 0 (none) or 1 (mild) for approximately 24h (as in the definition of time [hours] to resolution). • Recurrence identified if any of the individual RSV concepts comprising the RSV summary parameter scored >1 = 'not resolved' following previous resolution. 
Subjects will be evaluated over the course of the study and categorized ONCE as follows:
 
 • Not Resolved: if, over entire study course, individual RSV concepts comprising the RSV summary parameter have not resolved • Resolved With Recurrence: following resolution, individual RSV concepts comprising the RSV summary parameter >1 based on any of the subsequent ObsRO assessments • Resolved Without Recurrence: once resolved, individual RSV concepts comprising the RSV summary parameter maintained at 0 (none) or 1 (mild) based on subsequent ObsRO assessments

Measurement	Formula																																				
CLINICIAN PRESORS: ClinRO																																					

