For the RSV summary parameters specified in Section 5.4.1, these time to event variables will be analyzed using Kaplan-Meier analysis. Both the 80% and 95% 2-sided confidence intervals will be presented.

In addition, the RSV summary parameters will be further explored utilizing a similar AFT model as detailed for time (hours) to resolution in Section 5.3.2.2.

Graphical presentation will include:

- Overlay of survival curves with Kaplan-Meier survival function and AFT on one plot
- Forest plot of accelerated failure time ratios and resulting confidence intervals for subgroups of interest as defined in Section 2.4 including the relevant subgroup variable as covariate in the model with subgroup*treatment group interaction.

The aforementioned will be presented overall by treatment group and by the subgroups as defined in Section 2.4.

Association Between PRESORS: ObsRO: Time (hours) to Resolution: 24h Supplementation Free Definition and Covariates/Baseline Indicators

The potential association between the time (hours) to resolution: 24h supplementation free definition of summary parameter, PRESORS ObsRO: key RSV symptoms and covariates/baseline indicators of interest, as detailed in Section 5.3.2.1, will be explored utilizing a similar AFT model as described in Section 5.3.2.3.2, but including the relevant subgroup variable as covariate in the model with subgroup*treatment group interaction.

PRESORS ObsRO: Sustained Resolution

Proportion (number [n] and percentage [%]) of subjects per individual categories will be presented, as frequency tabulation and graphically, by treatment group. Additionally, 95% 2-sided confidence interval for each binomial proportion within the individual categories will be presented as based on the Wilson score test.

The aforementioned will be presented overall by treatment group and by the subgroups as defined in Section 2.4.

PRESORS ObsRO/ClinRO: Key RSV Symptoms: AUC

With reference to Section 5.2.3, a similar model as used for the primary efficacy analysis at Day 5 will be used for analysis of Day X ($AUC_{Day\ X}$), Day 8 ($AUC_{Day\ 8}$) and additionally for PRESORS ObsRO, Day 10 ($AUC_{Day\ 10}$). Where Day X is defined as the day when at least 50% of Cohort 1 subjects, across all treatment groups, have been discharged from hospital.

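### The exploratory sustained-resolution classes have no equal follow-up after resolution and no handling of missing diary entries, so they partly reflect speed of recovery and diary completeness

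*SAP*

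**What the plan says.** SAP section 5.4.1, Table 22, covers key and overall RSV symptoms: "Sustained resolution, assessed over entire study course, is defined as no evidence of recurrence once resolution has been reached". Each child receives one of three classes. The first is "Not Resolved: if, over entire study course, individual RSV concepts comprising the RSV summary parameter have not resolved". The second is "Resolved With Recurrence: following resolution, individual RSV concepts comprising the RSV summary parameter >1 based on any of the subsequent ObsRO assessments". The third is resolution maintained at 0 or 1 on whatever later entries exist.

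Resolution itself needs all component concepts at 0 or 1 for about 24 hours. In the twice-daily period this means, per section 5.3.1.2.1 (Table 17), "Three consecutive recordings indicating resolution are required". From the second Day 14 timepoint on, two suffice. Recurrence needs one concept above 1 on one entry.

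Table 4 in section 2.1.4 sets the caregiver (ObsRO) schedule: "BID from Day 1 to Day 14 and QD from Day 15 to Day 21".

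The analysis in section 5.4.2 is "Proportion (number [n] and percentage [%]) of subjects per individual categories will be presented, as frequency tabulation and graphically, by treatment group", with a Wilson 95% interval for each class and repetition by subgroup. Section 5.4 states that these additional exploratory endpoints support development decisions and health-authority interactions.

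**The concern.** Recurrence can only be recorded on entries made after resolution, and the number of these is not fixed. A child who resolves early has many; one who resolves late, or whose caregiver stops the diary, has few. Two children with the same tendency to relapse can therefore have different chances of being classed as recurrent.

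Missing entries act in the favourable direction. The definition rests on absence of evidence of recurrence, so a child who resolves and then has no further entries falls into Resolved Without Recurrence. The daily resolved-status rows of Table 22 have a MISSING class, and section 5.3.2.2 gives time to resolution four imputation sensitivity analyses. This endpoint has neither. Table 17 itself foresees ObsRO information missing because of (re-)hospitalization; a child who resolved, was readmitted and had no later entries would count as sustained.

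At stake is the reading of a durability table that the SAP says will inform development decisions.

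**Working it through.** **Inputs.** The schedule (Tables 4 and 5) gives 26 twice-daily target times after baseline, 12 h to 312 h, plus 7 daily entries: 33 in all. The planning effect (section 1.4, Cohort 1) is "assuming a median time to resolution of symptoms of 3 days in the placebo group, a 1-day reduction in the active group". The same paragraph gives the operating characteristic as "a scale parameter of 1/0.65, a sample size of 48 subjects per treatment arm will achieve 95% probability to reach an observed effect", meaning an estimate that favours active treatment. The SAP gives no chance per entry, h, of a score above 1 after resolution. It is assumed constant and independent, and varied from 0.25% to 10%. No entries are taken as missing unless stated.

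**Step 1: reproduce the plan's figure.** P = Φ(|ln ratio| / SE), with SE = √(2v/48). For a log-logistic model with σ = 0.65, v = (π × 0.65)²/3 = 1.39, so SE = 0.241. With ln(2/3) = −0.405, P = Φ(1.68) = 95.4%. Using v = 3 × 0.65² = 1.27 gives 96.1%. Both agree with the stated 95%. Reading σ as 1/0.65 gives 76% to 78% and does not. The log-logistic with medians 72 h and 48 h and σ = 0.65 is used below.

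**Step 2: entries left after confirmed resolution.** If resolution starts at twice-daily slot i, entries left = 33 − (i + 2). At 312 h (slot 26) the two-recording rule gives 33 − 27. P(recurrence) = 1 − (1 − h)^k for k entries left.

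| First resolved at | Entries left | P at h = 2% |
|---|---|---|
| 48 h | 27 | 42.0% |
| 72 h | 25 | 39.7% |
| 168 h | 17 | 29.1% |
| 240 h | 11 | 19.9% |
| 312 h | 6 | 11.4% |

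Between individual children the spread is wide. Between the planned medians it is 27 versus 25 entries.

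**Step 3: arm against arm.** With 200,000 draws per arm and the same h in both arms, mean entries left among resolvers are 22.6 (slower) and 24.6 (faster). Not Resolved is 5.5% and 3.0%.

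| h | Recurrence among resolvers, slower vs faster | Resolved Without Recurrence, of all children, slower vs faster |
|---|---|---|
| 0.5% | 10.7% vs 11.6% | 84.5% vs 85.8% |
| 1% | 20.1% vs 21.7% | 75.5% vs 75.9% |
| 2% | 36.0% vs 38.7% | 60.5% vs 59.5% |
| 5% | 66.2% vs 70.0% | 31.9% vs 29.1% |

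The largest gap among resolvers at any h tried is 3.8 points. With placebo medians of 5 to 10 days and the same 1-day gain, it is 0.5 to 2.8 points (h = 1% to 5%). For scale, the 95% half-width for one arm of 48 is about 9 to 14 points for h = 0.5% to 5%.

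**Step 4: stopped diaries.** At h = 2%, a child resolved at 48 h has a 42.0% chance of being classed as recurrent with a full diary. If the diary stops after 7 further entries the chance is 1 − 0.98⁷ = 13.2%; with none it is 0.

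**Step 5: single-entry rule.** At h = 2%, over a third of resolvers in either arm are classed as recurrent. If stray high entries are independent, three in a row at given entries have probability 0.02³ = 0.000008. Confirmation would thus remove nearly all isolated entries.

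**Step 6: equal follow-up.** Counting only the next 6 entries after resolution, the arm gap among resolvers is 0.1 to 0.3 points for h = 1% to 5%. With the next 14 it is 0.3 to 1.1, against 1.6 to 3.8 with no cap.

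**The case against.** A reader might infer that an effective drug will look clearly less durable, by the 30 points or so that separate a child resolved at 48 h from one resolved at 312 h. The documents do not support that. The planning effect in section 1.4 and the target value in section 5.6 are both one day, so the arms differ by about 2 entries, not 21. A faster drug also moves children out of Not Resolved. Over all children, the sustained proportion then favours the faster arm slightly at h = 0.5% and 1%. If recurrence is concentrated soon after resolution, the gap falls to about 1 point or less.

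A reader might also infer a formal comparison of arms on this endpoint. Section 5.4.2 plans frequencies, a graph and an interval per class, with no difference and no test. The endpoint is exploratory and is not among the key endpoints in the section 5.6 decision rules. Speed of recovery is analysed separately by Kaplan-Meier and accelerated failure time models, and missing ObsRO entries are tabulated by visit window, treatment group and cohort.

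Whether a child stayed resolved to the end of the diary is a legitimate descriptive question. Any alternative still conditions on having resolved, so it does not restore a randomised comparison.

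All of this stands, and it limits the size of the point. It does not answer the unequal follow-up, or the scoring of children with few or no later entries as sustained: separate missing-data tables do not change that class.

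**Conclusion.** The point holds as a cheap improvement. The three classes mix durability with time of resolution and diary completeness. Between arms, the expected distortion at the planned effect is small: at most about 4 points among resolvers, well inside the sampling error of 48 per arm, and of either sign over all children. It is larger where children differ more in resolution time or diary completeness. This could matter for the subgroup tables, although the SAP gives no figures to size it there.

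The figures rest on an assumed constant, independent risk per entry, on complete diaries except in Step 4, and on the Cohort 1 planning distribution applied to both summary parameters.

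**What to change.** Keep the three-class table and add, in sections 5.4.1 and 5.4.2:

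- a Kaplan-Meier display by arm of time from resolution to first recurrence, censored at the last ObsRO entry; or recurrence within a fixed window, for example 7 days after resolution;
- a separate class for resolved children with incomplete follow-up, including those with no later entries;
- optionally, a sensitivity analysis requiring recurrence to be confirmed over about 24 hours, as resolution is.

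The data are already collected. The cost is one extra exploratory output and a few lines of derivation. Late resolvers are not evaluable in a fixed window, and the change from twice-daily to daily entries after Day 14 means that equal days are not exactly equal entries. The output should state that it conditions on having resolved.

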5.4.2. Analysis Methods

PRESORS ObsRO: RSV Recovery Scale (RRS): Day 1 to Day 8

The RRS will be assessed from Day 1 to Day 8. The proportion (number [n] and percentage [%]) of subjects per ordered categories will be presented, as frequency tabulation and graphically, by treatment group and study day.

The proportional odds model will be used to analyze the RRS Day 2 to Day 8, modeling the common odds ratio (cOR) of improvement on the ordinal scale of each active treatment group versus placebo. Ordered logistic regression model will include treatment group, baseline RRS category and the two randomization stratification factors (derived). The proportional odds model will be defined in such a way that a $\text{cOR} < 1$ indicates larger improvement in the active treatment group.

The aforementioned will be presented overall by treatment group and by the subgroups as defined in Section 2.4.

Resolved Status Based on PRESORS ObsRO/ClinRO: Day 1 to Day 8, Resolved Status Based on PRESORS ObsRO/ClinRO Before/After Hospital Discharge

Proportion (number [n] and percentage [%]) of subjects per individual categories will be presented graphically, by treatment group.

The aforementioned will be presented overall by treatment group and by the subgroups as defined in Section 2.4.

PRESORS ClinRO: Clinically Resolved Status: Day 1 to Day 8

Clinically resolved status, will be assessed from Day 1 to Day 8. The proportion (number [n] and percentage [%]) of subjects per individual categories will be presented, as frequency tabulation and graphically, by treatment group and study day.

A logistic regression model will be used to analyze the binary dependent variable, clinically resolved status Day 2 to Day 8, comparing each active treatment group versus placebo. Logistic regression model will include treatment group and the two randomization stratification factors (derived). Estimate of the treatment difference in proportion of clinically resolved status and both 80% and 95% 2-sided confidence intervals for this estimate will be obtained from the logistic regression model.

The aforementioned will be presented overall by treatment group and by the subgroups as defined in Section 2.4.

A sensitivity analysis will be performed applying the alternative imputed value (Column 4: Sensitivity analysis imputed value [Section 5.4.1]).

PRESORS ObsRO/ClinRO: Time to Resolution [Supplemental-free Definitions] and PRESORS ObsRO: Time to Resolution From Hospital Discharge

For the RSV summary parameters specified in Section 5.4.1, these time to event variables will be analyzed using Kaplan-Meier analysis. Both the 80% and 95% 2-sided confidence intervals will be presented.

In addition, the RSV summary parameters will be further explored utilizing a similar AFT model as detailed for time (hours) to resolution in Section 5.3.2.2.

Graphical presentation will include:

- Overlay of survival curves with Kaplan-Meier survival function and AFT on one plot
- Forest plot of accelerated failure time ratios and resulting confidence intervals for subgroups of interest as defined in Section 2.4 including the relevant subgroup variable as covariate in the model with subgroup*treatment group interaction.

The aforementioned will be presented overall by treatment group and by the subgroups as defined in Section 2.4.

Association Between PRESORS: ObsRO: Time (hours) to Resolution: 24h Supplementation Free Definition and Covariates/Baseline Indicators

The potential association between the time (hours) to resolution: 24h supplementation free definition of summary parameter, PRESORS ObsRO: key RSV symptoms and covariates/baseline indicators of interest, as detailed in Section 5.3.2.1, will be explored utilizing a similar AFT model as described in Section 5.3.2.3.2, but including the relevant subgroup variable as covariate in the model with subgroup*treatment group interaction.

PRESORS ObsRO: Sustained Resolution

Proportion (number [n] and percentage [%]) of subjects per individual categories will be presented, as frequency tabulation and graphically, by treatment group. Additionally, 95% 2-sided confidence interval for each binomial proportion within the individual categories will be presented as based on the Wilson score test.

The aforementioned will be presented overall by treatment group and by the subgroups as defined in Section 2.4.

PRESORS ObsRO/ClinRO: Key RSV Symptoms: AUC

With reference to Section 5.2.3, a similar model as used for the primary efficacy analysis at Day 5 will be used for analysis of Day X ($AUC_{Day\ X}$), Day 8 ($AUC_{Day\ 8}$) and additionally for PRESORS ObsRO, Day 10 ($AUC_{Day\ 10}$). Where Day X is defined as the day when at least 50% of Cohort 1 subjects, across all treatment groups, have been discharged from hospital.

The difference between each active treatment group versus placebo will be derived using appropriate contrasts for Day X, Day 8 and Day 10 (PRESORS ObsRO only) from the same model containing all PRESORS ObsRO/ClinRO assessments from baseline through assessment day of interest (ObsRO: Day 10, ClinRO: Day 8).

The aforementioned will be presented for the subgroups as defined in Section 2.4.

RSV-related Complications

RSV-related complications will be provided based on the original (investigator assessment) and modified (study physician-identified complications) definitions.

Original Definition (Investigator Assessment):

The proportion of subjects with a complication (Yes and No) will be shown in a frequency tabulation including corresponding 95% CI by treatment as based on the Wilson score test.

Based on the binary categorization (Yes vs No), the difference in proportion of subjects with RSV-related complications, as assessed by the investigator, between each active treatment group as compared to placebo will be investigated. Frequency procedure in SAS® provides Newcombe confidence limits with Mantel-Haenszel weights for the common risk difference (difference in proportion of subjects with RSV-related complications), controlling for the two randomization stratification factors (separately). The difference in proportion of subjects with RSV-related complications and 80% and 95% 2-sided confidence intervals for this point estimate, controlling for randomization stratification factors, will be presented.

Similar frequency tables will be provided for the subcategories.

The aforementioned summary will be presented overall by treatment group and by the subgroups as defined in Section 2.4.

Modified Definition (Study Physician-identified Complications):

The number (n) and percentage (%) of subjects in the ITT-i analysis set with RSV-related complications (Yes vs No) will be presented, as frequency tabulation. The incidence will

be presented for emergent adverse events (treatment phase and follow-up phase), as assessed by the study physician (modified definition), occurring during the study and treatment phase only.

The number (n) and percentage (%) of subjects, by MedDRA preferred term, in each of the subcategories will also be presented.

Based on the binary categorization (Yes vs No), the difference in proportion of subjects with RSV-related complications, modified definition, between each active treatment group as compared to placebo will be investigated and presented in a similar manner as described above.

The aforementioned summary will be presented overall by treatment group and by the subgroups as defined in Section 2.4.

Use of Antibiotics for RSV-related Complications: Investigator Assessment

The proportion (number [n] and percentage [%]) of subjects using antibiotics for RSV-related complications at any time during the study (treatment phase and follow-up phase) will be presented, as frequency tabulation and graphically, by treatment group. Additionally, 95% 2-sided confidence interval for each binomial proportion within the individual categories (Yes vs No) will be presented as based on the Wilson score test.

The aforementioned will be presented overall by treatment group and by the subgroups as defined in Section 2.4.

